#### IV. STUDY DESIGN

This study is a pilot randomized control trial that aims to assess feasibility and explore or test (if possible) outcomes of waterbirth to that of conventional land birth for low-risk healthy women and neonates in a hospital setting in Milwaukee, WI. Low-risk healthy adult women will be enrolled from January 2022 through December 2025. The study could be introduced to potentially eligible women in their second trimester. Patient recruitment materials will also be placed in the waiting room and exam rooms. Patient recruitment materials will be created upon receipt of the birthing tub (October 2021) and will be approved by the IRB prior to use. We have attached the recruitment poster for approval.

We plan to enroll women using a random allocation rule in the ratio 2:1, with two women randomized to the waterbirth group for every one woman randomized to the land birth group. Women will be randomized in the Midwifery and Wellness Clinic, Exclusively for Women, and the Women's Health Clinic at Aurora Sinai Medical Center at the beginning of the third trimester (25 weeks 0 days to 34 weeks 0 days gestation) upon consent by the research coordinator, faculty physician(s), or midwives listed on this study. Consent will be documented with a dotphrase (.waterbirthconsent2; Appendix A). Patients will be presented with a sealed envelope which will contain a slip of paper identifying the patient's random assignment to either the waterbirth or land birth (again with a 2:1 randomization allocation). Currently, randomization is completed through REDcap.

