## VII. STATISTICAL PLAN

The **primary outcome** we seek is a reduction of IV narcotic and epidural anesthesia use. We anticipate that this pilot project would be powered to detect a very clinically meaningful percentage point reduction in use of IV narcotic and epidural anesthesia. We carried out a power analysis using G\*Power 3.1.9.6. Using the Fleiss methodology to estimate power calculations with 80% power at the 0.05 level of significance, we estimate the following: to detect about 80% reduction in IV narcotic use from 24.5% down to 5.5%, estimated need would be 68 in the waterbirth group, 34 in the control group. To detect about 40% reduction in epidural use from 59% down to 34%, estimated need would be 74 in the waterbirth group, 37 in the control group. We have recalculated our sample sized based on the current enrollment attrition rate of 39.4%

(rate in which patients risk out of the study). With a 2:1 allocation ratio, approximately 120 subjects were initially earmarked to be recruited into the study given 74 would be needed in the waterbirth group and 37 would be needed in the land birth group to detect a 40% reduction in epidural use. Following the recommendations of Sakpal, we used the attrition rate (rate in which patients risk out of the study) to calculate adjusted sample sizes as 124 in the waterbirth group and 62 in the land birth group for a total of 186. We continue to approach most pregnant people eligible for waterbirth with the understanding that some will not want to participate in a research study. The results of this pilot should inform sample size required for a larger, definitive study that would be powered to detect smaller, still meaningful reductions in narcotic/epidural use.

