We will compare baseline characteristics and pre-determined outcomes between patients who are randomized to either waterbirth or land birth. We will compute frequencies, means with 95% confidence intervals, and medians with interquartile ranges, as appropriate per variable type. Differences among the groups will be tested using the Pearson chi-squared test of independence (or Fisher's exact), Student's t-test, or Wilcoxon's rank sum test, respectively. Continuous variables will be assessed for normal distribution. Categorical variables will be assessed for collinearity. Potentially, we will use logistic regression for binary categorical outcomes (e.g., opioid use/anesthetist intervention, maternal tears, vaginal birth versus conversion to cesarean section, etc.) and linear regression for continuous outcomes (e.g., blood loss, time to skin-to-skin contact, etc.). Potentially, we will also perform ordered logistic regression on ordinal outcomes such as satisfaction level and APGAR. All underlying assumptions will be tested for each statistical method used. A one tailed p value lower than 0.05 will be considered statistically significant.

Please note, a data safety monitoring plan has been created for this study and is included in Appendix D. The first ten subjects that are enrolled for a waterbirth will be monitored and reviewed by the study PI, co-investigators, and Maternal Newborn Quality Committee for any rare adverse outcomes. For all subjects, the Principal Investigator and co-investigators will continue to review all adverse outcomes and will regularly monitor the data to identify trends throughout the study.

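### Student's pooled t-test is named for continuous outcomes under 2:1 allocation, with no action stated if variances differ; Welch's test should be the default wherever a t-test is used

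*Combined protocol and SAP*

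**What the plan says.** Section IV (Study Design) sets unequal allocation: "We plan to enroll women using a random allocation rule in the ratio 2:1", with waterbirth the larger arm. Section VII (Statistical Plan) works from an evaluable requirement for epidural use, where "estimated need would be 74 in the waterbirth group, 37 in the control group", and then inflates for women who risk out, giving "adjusted sample sizes as 124 in the waterbirth group and 62 in the land birth group for a total of 186".

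For between-arm comparisons, the same section lists a chi-squared or Fisher test for categorical variables. For the rest it lists "Student's t-test, or Wilcoxon's rank sum test", chosen by variable type after a normality check. Linear regression for continuous outcomes, and ordered logistic regression for outcomes such as satisfaction, are mentioned as possibilities only. Two further sentences matter here: "All underlying assumptions will be tested for each statistical method used" and "A one tailed p value lower than 0.05 will be considered statistically significant".

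Welch's test is not named anywhere. The plan does not say what happens if the equal-variance assumption fails.

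**The concern.** Student's test estimates one common variance. With equal arms, a difference in spread hardly affects its error rate. At 2:1 the larger arm dominates the pooled variance, while the smaller arm contributes most to the true uncertainty. If the land arm is the more variable one, the pooled standard error is too small and false positives rise. If the waterbirth arm is, the standard error is too large and the test becomes conservative.

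Unequal spread is plausible, but its direction is not known. The plan expects the arms to differ in epidural use (59% against 34%), in operative delivery and in labor duration, any of which could widen the land arm. Women who switch from water to land could instead widen the waterbirth arm.

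The outcomes at stake are secondary continuous ones, such as labor duration and blood loss, where they are close enough to normal for a t-test. An ordinary linear regression on arm carries the same equal-variance assumption. The pilot is meant to inform a larger trial and possibly meta-analyses, so these results may be reused.

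**Working it through.** **Inputs.** Evaluable sizes 74 and 37, inflated sizes 124 and 62, one-tailed 0.05 (all Section VII); 2:1 allocation (Section IV). The SD ratio is an assumption and is varied.

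**The plan's own figures.** A one-sided normal-approximation calculation for 59% against 34% at 2:1, without continuity correction, gives 72 and 36, close to the stated 74 and 37. For attrition of 39.4%, 37/0.606 = 61.06, rounded up to 62, and 2 × 62 = 124, as stated. With equal SDs, Student's test has the stated 5% level: 400,000 simulated normal trials with no true difference gave 4.98% at 74/37 and 4.96% at 124/62.

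**Effect of unequal SDs.** Let the variances be v_w (water) and v_l (land).

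- Pooled SE² = [(73 v_w + 36 v_l)/109] × (1/74 + 1/37)
- True SE² = v_w/74 + v_l/37
- Large-sample one-tailed error = 1 − Φ(1.659 × SE_pooled/SE_true), where 1.659 is the 95% point of t on 109 df

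Example, land SD 1.5 times water SD: the pooled variance is (73 + 36 × 2.25)/109 = 1.413. Pooled SE² = 1.413 × 0.04054 = 0.0573. True SE² = 0.0135 + 0.0608 = 0.0743. The SE ratio is √(0.0573/0.0743) = 0.878, so the standard error is about 12% too small. The error is 1 − Φ(1.456), about 7.3%.

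| More variable arm | Pooled SE² | True SE² | SE ratio | Formula | Simulated |
|---|---|---|---|---|---|
| Land, 2x | 0.0807 | 0.1216 | 0.815 | 8.8% | 9.0% to 9.1% |
| Land, 1.5x | 0.0573 | 0.0743 | 0.878 | 7.3% | about 7.5% |
| Land, 1.25x | 0.0481 | 0.0557 | 0.929 | 6.2% | 6.1% to 6.3% |
| Water, 1.25x | 0.0558 | 0.0481 | 1.077 | 3.7% | 3.8% to 3.9% |
| Water, 1.5x | 0.0745 | 0.0574 | 1.139 | 2.9% | 3.0% to 3.1% |
| Water, 2x | 0.1220 | 0.0811 | 1.227 | 2.1% | 2.2% to 2.3% |

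The larger sample does not help: at 124/62 a two-fold difference gives 9.0% and 2.2%. With equal arms of 55 the error stays at 5.0% to 5.1% for SD ratios from 1/3 to 3, so the unequal allocation is what lets unequal spread do harm.

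**Alternatives, normal data.** Welch's test gives 4.95% to 5.10% at both sizes for every SD ratio from 1/3 to 3. Wilcoxon, the only other test named, gives about 7.6% (land SD 2x) and 3.5% (water SD 2x) at 74/37, so it is not a remedy for unequal spread. If SDs are equal, power at a standardized difference of 0.5 is 79.5% for Student and 79.2% for Welch.

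**If the assumption check led to Welch (an assumed step).** An F-test at 5% followed by Welch on rejection gives 4.5% to 5.6%. Levene's test used the same way gives 4.3% to about 5.7% (200,000 simulated trials per setting). Levene's test detects a two-fold difference about 99% of the time, but a 1.25-fold difference only about 28%.

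**Skewed data with identical distributions in both arms, 74/37.** For a lognormal with log-SD 0.5, Welch's two one-sided errors are about 3.9% (water looking lower) and 6.3% (water looking higher), against about 5.3% and 4.6% for Student. At log-SD 1.0 they are about 2.8% and 7.6%, against 5.8% and 3.9%.

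**The case against.** The best defense is the promise to test every method's assumptions, which for Student's test includes equal variances. Large differences in spread would almost always be found, and the differences that are missed do little harm. A test-then-Welch rule performs acceptably, as shown above. What stands of this is that the exposure is small if the check has that consequence. The plan states no consequence, and the one alternative it names is itself off under unequal spread.

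Two further objections stand and limit the point. Welch is not better everywhere: with skewed data of equal spread at 2:1 it is further from 5% in each tail than Student. And this is a pilot that tests hypotheses only if its sample permits.

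A reader might also infer more than the documents support:

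- That any difference in spread moves the error to 2% or 9%. That range needs a two-fold SD difference; at 1.25-fold the shift is about one point.
- That the primary result is affected. IV narcotic and epidural use are binary and are not compared with a t-test.
- That labor duration, blood loss and the US-BSS-R are all committed to Student's test. The choice depends on variable type and normality, and satisfaction may go to ordered logistic regression.

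**Conclusion.** The point holds in a limited form. Where a t-test is used for a secondary continuous outcome, the plan names the pooled version under 2:1 allocation and gives no rule for unequal variances. On normal data the one-tailed error would be about 3.8% to 6.3%, 3.0% to 7.5% or 2.2% to 9.1% for SD ratios of 1.25, 1.5 or 2. The direction depends on which arm varies more. These ratios are assumed, and the documents give nothing from which to judge the true ones. The calculation takes Student's test in its usual pooled sense. It is a small, easily removed weakness in the secondary analyses, not a threat to the trial's main comparison.

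**What to change.** In the Statistical Plan:

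- Replace Student's t-test with Welch's unequal-variance t-test as the default wherever a t-test is used, without a preliminary test of variances.
- If linear regression is used, specify heteroscedasticity-robust standard errors (for example HC3).
- Keep the Wilcoxon rank sum test, or a transformation, for clearly skewed variables. Do not present Wilcoxon as the answer to unequal variances.

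This takes a sentence or two and needs no data or participants. It costs about 0.3 points of power if the variances are equal, and slightly worse balance between the tails than Student under mild skewness with equal spread.

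### The primary analysis is not fixed: the plan commits only to unadjusted tests and leaves regression optional with no covariates or rule, although parity is already collected and could be named for adjustment

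*Combined protocol and SAP*

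**What the plan says.** Section VII (Statistical Plan) gives the primary outcome as a reduction in IV narcotic and epidural use. Arms are to be compared, on baseline characteristics and outcomes alike, by Pearson chi-squared or Fisher's exact test, t-test or rank sum test. All of these are unadjusted. The plan then says "Potentially, we will use logistic regression for binary categorical outcomes". The first example given is opioid use or anesthetist intervention, which is in substance the primary outcome. No covariate is named, nothing says when regression would be used, and neither result is called primary. The decision rule is "A one tailed p value lower than 0.05 will be considered statistically significant".

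Section IV (Study Design) says "We plan to enroll women using a random allocation rule in the ratio 2:1". It names no stratification factor.

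The Data Collection section (also numbered VII) lists parity among the maternal variables. It does not say when parity is recorded; data elements are drawn from the delivery record and the midwifery database. The same section plans an interim analysis after the first year, with preliminary results presented at a scientific meeting.

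**The concern.** Two things are at stake.

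**Pre-specification.** An unadjusted test and an adjusted model of the same outcome can fall on opposite sides of the 0.05 threshold. The plan does not say which one decides, so the choice, and the choice of covariates, can be made after the data are seen. The year-one interim makes this more than theoretical.

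**Efficiency and chance imbalance.** If parity predicts epidural use, an unadjusted comparison gives up some precision that an already collected variable could supply. In a trial with about 37 women in the smaller arm and no stratification, the arms will quite often differ visibly in the share of nulliparous women. A reader would then ask for an adjusted result that the plan never defined.

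**Working it through.** **1. Reproduce the plan's sample size.** Inputs, all from the Statistical Plan: "Using the Fleiss methodology to estimate power calculations", "with 80% power at the 0.05 level of significance", and for epidural use "To detect about 40% reduction in epidural use from 59% down to 34" per cent. The result given is "estimated need would be 74 in the waterbirth group, 37 in the control group".

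With 2:1 allocation the land-arm size is

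n = [z_α √(1.5 p̄(1−p̄)) + z_0.80 √(p1(1−p1) + p2(1−p2)/2)]² / (p1−p2)².

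- One-sided 0.05, p̄ = (0.59+0.34)/2: n = 36.3, so 37 and 74. This matches.
- The same formula for IV narcotic (24.5% to 5.5%): n = 33.9, so 34 and 68. This matches.
- For epidural use, two-sided gives 46.1, and one-sided with continuity correction gives 42. Neither matches.
- Attrition: 37/(1−0.394) = 61.1, so 62; 2 × 62 = 124; total 186. This matches.

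The sizing is therefore for an unadjusted one-sided comparison of two proportions. Its power at 37 versus 74 is 81.1% by formula (80.6% exact).

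**2. Power with parity adjustment.** The documents give neither the share nulliparous nor any rate by parity. *Assumed:* 30-50% nulliparous and an odds ratio for epidural use (nulliparous versus parous) of 1 to 6, with marginal rates held at 59% and 34%. Simulation used 100,000 replicates per scenario, comparing the unadjusted chi-squared test with a parity-stratified Mantel-Haenszel test, one-sided 0.05. The variance ratio is that of the parity-standardised risk difference to the unadjusted one.

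| Assumed odds ratio | Unadjusted power | Adjusted power | Variance ratio |
|---|---|---|---|
| 1 | about 81% | 80.6-80.7% | about 1.015 |
| 1.5 | about 81% | 81.0-81.3% | 1.005-1.009 |
| 2 | about 81% | 81.4-81.9% | 0.985-0.99 |
| 3 | about 81% | 82.9-83.2% | 0.945-0.96 |
| 4 | about 81% | 83.9-84.4% | 0.905-0.93 |
| 6 | about 81% | 85.8-86.7% | 0.85-0.88 |

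A closed-form check agrees. Let f be the share nulliparous, d the gap in epidural use by parity, and 0.423 the pooled rate (0.59 + 2×0.34)/3. Then R² = f(1−f)d²/(0.423×0.577). With f = 0.4-0.5, gaps of 20, 30 and 40 points give R² of about 4%, 9% and 16%. Effective size rises by 1/(1−R²), about 4%, 10% and 19-20%, and power becomes about 83%, 84% and 87%. A 10-point gap gives 81.5%.

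**3. IV narcotic use.** Expected events at 34 and 68 are 0.245×34 = 8.3 and 0.055×68 = 3.7. With 40% nulliparous, simulated power is 86.5% unadjusted against 86.0% adjusted at odds ratio 1, and 86.5% against 87.3% at odds ratio 4. The gain here is below 1 point throughout that range.

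**4. Chance imbalance.** The SD of the arm difference in nulliparous share is √[f(1−f)(1/37+1/74)], which is 0.09-0.10 for f = 0.3-0.5. From the hypergeometric distribution, the difference is 10 points or more in 27-32% of randomisations at 37 versus 74, and in 16-20% at 62 versus 124. A one-SD imbalance of 10 points, times an assumed 20-40 point gap, moves the epidural contrast by 2-4 points. The target difference is 25 points, and the standard error is √(0.59×0.41/37 + 0.34×0.66/74) = 9.8 points.

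**5. Validity of the unadjusted test.** With no treatment effect, its simulated one-sided type I error is 4.6-5.1% across all scenarios.

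**The case against.** The strongest reply is that nothing here is broken. The unadjusted test holds its level, and its standard error already allows for chance imbalance in parity. The study is a pilot that will test its hypotheses only if numbers allow. Choosing adjustment is then a preference worth 0 to 6 power points, resting on a figure that the documents do not supply. All of that stands, and it limits the point to an improvement. It does not answer the pre-specification gap: even a pilot needs to say which of two possible analyses it will report as primary.

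The text also does not support several stronger readings that a reader might infer:

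- *That the plan fixes an unadjusted chi-squared test as the primary analysis.* It does not; regression is left open for this very outcome.
- *That adjustment will be triggered by baseline significance tests.* Baseline comparisons and optional regression appear in the same paragraph, but no sentence links them. There is simply no rule.
- *That parity is documented as prognostic, or as recorded at baseline.* Neither is stated. Parity before the index birth is fixed before randomisation, but the plan should define the variable that way.
- *That a parity imbalance would invalidate the unadjusted result.* Step 5 shows otherwise.

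A practical objection also stands: changing the primary model during the trial is not free of risk if results by arm have already been seen.

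**Conclusion.** The point holds as an efficiency and pre-specification improvement. What is certain from the documents is that only unadjusted tests are committed to, regression is optional without covariates or a rule, no stratification is described, and parity is collected. The size of the precision gain is conditional. For epidural use it is about 1 power point or less at an assumed odds ratio of 2 or below, and about 2-6 points at 3-6. If parity does not matter, the cost is about 1.5% in variance. For IV narcotic use there is little to gain. The imbalance figure of 27-32% assumes 30-50% nulliparous and an analysed set of 37 and 74 that is still a random split. Women found ineligible after randomisation are dropped without further data (Section IV), so that last condition is not guaranteed, and parity adjustment would address it only for parity.

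**What to change.** In the Statistical Plan:

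- Name one primary analysis for each stated component, epidural use and IV narcotic use: the risk difference between arms adjusted for parity (nulliparous versus parous). Estimate it by Mantel-Haenszel, or by logistic regression with arm and parity standardised to the marginal scale. Either keeps the result on the scale of the 59% and 34% planning rates.
- For IV narcotic use, prefer Mantel-Haenszel or an exact stratified test, because only about 12 events are expected (8.3 + 3.7).
- Define parity as the value before the index birth.
- Keep the unadjusted Pearson or Fisher test as a sensitivity analysis.
- For labor duration, which is continuous, use linear regression with arm and parity, transformed if skewed.
- Report baseline characteristics descriptively, without significance tests.

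Record this in a dated amendment made without knowledge of results by arm. Because a year-one interim is planned, the amendment should state whether anyone deciding has seen such results. The cost is this wording and that documented decision; no new data, visits or participants are needed.

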## II. SPECIFIC AIMS

The proposed pilot randomized control trial will be approached as a feasibility study to explore or test (if sample size permits) our hypotheses. Additional sample size analyses have been conducted since this study was first submitted as we continue to explore the feasibility of this study in hopes of answering our primary outcome.

**Primary outcome:** Women in the waterbirth group will use less IV narcotic and epidural anesthesia than women in the land birth group.

We further seek to address the following additional specific aims:

**Specific Aim 1:** Evaluate waterbirth outcomes in adult low-risk laboring women randomized to waterbirth in comparison to women randomized to birth on land.

**Hypothesis 1a.** Women in the waterbirth cohort will have shorter labor duration than women in the land cohort.

**Hypothesis 1b.** Women in the waterbirth cohort will be more likely to initiate breastfeeding before discharge.

**Specific Aim 2:** Evaluate the safety of waterbirth in adult low-risk laboring women randomized to waterbirth in comparison to women randomized to birth on land.

**Hypothesis 2a.** Women in the waterbirth cohort will not experience more adverse outcomes (e.g., postpartum hemorrhage, third- or fourth-degree perineal lacerations, etc.) than women in the control group.

**Specific Aim 3:** Evaluate satisfaction with waterbirth in adult low-risk laboring women randomized to waterbirth in comparison to women randomized to birth on land.

**Hypothesis 3.** Women in the waterbirth cohort will experience greater satisfaction scores on the revised United States Birth Satisfaction Scale-Revised (US-BSS-R), than women in the land cohort.

**Specific Aim 4:** Evaluate the safety of waterbirth for term low-risk neonates in comparison to land birth term low-risk neonates.

**Hypothesis 4a.** Infants in the waterbirth group will not experience more adverse outcomes (e.g., NICU admission, APGAR scores <7, umbilical cord injury, etc.) than infants born to women in the land cohort.

**Hypothesis 4b.** Infants in the waterbirth group will experience fewer instrumental (e.g., forceps, vacuum, etc.) or cesarean deliveries.

**Hypothesis 4c.** Infants born to women in the waterbirth cohort will have immediate skin-to-skin contact.

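### The two safety hypotheses claim no excess of adverse outcomes, but the plan offers only difference tests under a one-tailed rule, which cannot support that claim

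*Combined protocol and SAP*

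**What the plan says.** Section II (Specific Aims) sets two safety hypotheses. Hypothesis 2a reads "Women in the waterbirth cohort will not experience more adverse outcomes" and Hypothesis 4a reads "Infants in the waterbirth group will not experience more adverse outcomes", each against the land group. Neither carries a margin, and the outcomes are given as examples rather than as a closed list.

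Section VII (Statistical Plan) describes one analysis for all outcomes. For categorical data, "Differences among the groups will be tested using the Pearson chi-squared test of independence (or Fisher's exact" is the operative text. Regression is mentioned only as a possibility. The summaries are described as "We will compute frequencies, means with 95% confidence intervals, and medians with interquartile ranges", so the only intervals named are those for means. The decision rule is "A one tailed p value lower than 0.05 will be considered statistically significant". No direction is given and no outcome is exempted.

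The sample size rests on analgesia alone, "with 80% power at the 0.05 level of significance". The figure carried forward is for "about 40% reduction in epidural use from 59% down to 34%, estimated need would be 74 in the waterbirth group, 37" on land. There is no power, precision or margin for any adverse outcome.

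**The concern.** The hypotheses and the test point in different directions. A hypothesis of no excess harm is supported only by ruling out an excess of a stated size, or by showing an interval whose upper limit is tolerable. A test of difference starts from equality and can only reject it. Failing to reject leaves open everything from benefit to substantial harm, and with few events failure to reject is the likely result whatever the truth.

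The missing tail direction adds to this. The primary hypothesis predicts less analgesia with waterbirth. If the same tail were carried over to adverse outcomes, an excess in the waterbirth arm could not reach significance at any size.

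Safety accounts for two of the four specific aims, and Section I calls neonatal risk the most disputed aspect of waterbirth. Without a rule for what would support 2a or 4a, the conclusion is left to whoever writes the report, who would have a p-value that says little.

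**Working it through.** **1. The plan's own figure.** Fleiss formula without continuity correction, r = 2 waterbirth per land, p̄ = (p1 + r·p2)/(1 + r):

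n(land) = [zα·√((1 + 1/r)·p̄(1 − p̄)) + zβ·√(p1(1 − p1) + p2(1 − p2)/r)]² / (p1 − p2)²

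With p1 = 0.59, p2 = 0.34, p̄ = (0.59 + 0.68)/3 = 0.423 and zβ = 0.842:
- one-sided 0.05 (zα = 1.645): 35.8, so 36 land and 72 waterbirth, close to the stated 37 and 74;
- two-sided 0.05 (zα = 1.960): 45.5, so 46 and 92.

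The epidural size therefore agrees with a one-sided test. Inflation for 39.4% risk-out gives 37/(1 − 0.394) = 61.1, so 62; doubled, 124; total 186, as stated. None of this concerns adverse outcomes.

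**2. Denominators.** Section IV says that no further data are collected on women who become ineligible, which returns the evaluable numbers to about 74 and 37. Section III keeps women excluded by the birth attendant in their assigned group under intention to treat. Both 74/37 and 124/62 are therefore shown.

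**3. Chance of detecting a true doubling of harm.** Land rates are assumed (2%, 5%, 10%), since the documents give none. Power is the sum, over all x land and y waterbirth events, of Bin(x; nL, p)·Bin(y; nW, 2p), counting only tables that reject toward harm. For Pearson this means z = (y/nW − x/nL)/√(p̄(1 − p̄)(1/nW + 1/nL)) > 1.645, where p̄ = (x + y)/(nL + nW). For Fisher it means an upper hypergeometric tail < 0.05.

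| Land → water rate | 74/37 Pearson | 74/37 Fisher | 124/62 Pearson | 124/62 Fisher |
|---|---|---|---|---|
| 2% → 4% | 3.6% | 0.5% | 12% | 4% |
| 5% → 10% | 18% | 11% | 30% | 21% |
| 10% → 20% | 36% | 29% | 54% | 47% |

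At 74/37 a real doubling is non-significant from 64% (100 − 36) to over 99% of the time, even with the tail pointing to harm.

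**4. What sparse data leave open.** Zero events in 74 waterbirths has a two-sided 95% upper limit of 1 − 0.025^(1/74) = 4.9%.

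The approximate 95% half-width for a risk difference at 74/37 is 1.96·√(p(1 − p)(1/74 + 1/37)). This gives 6.7, 8.6 and 11.8 percentage points at common rates of 3%, 5% and 10%.

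**5. A worked table.** Take 7 events in 74 waterbirths (9.5%) and none in 37 land births. The expected land count is 7 × 37/111 = 2.3, so Fisher's test is the usual choice. One-tailed toward harm it gives p = 0.053, not significant; eight events would be needed.

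For the Newcombe interval, the Wilson limits are 4.7% to 18.3% for 7/74 and 0% to 9.4% for 0/37:
- lower: 9.5 − √((9.5 − 4.7)² + 9.4²) ≈ −1.1 points;
- upper: 9.5 + (18.3 − 9.5) = 18.3 points.

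The p-value alone gives no warning. The interval shows that an excess of up to about 18 points has not been excluded.

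**The case against.** The strongest reply is that this is a pilot. Section II says the hypotheses will be explored, and tested only where numbers allow. Section III says the size needed for testing is still to be determined and that the data may feed a larger trial or a meta-analysis. The plan never claims power for safety. Participants are also protected by the case review in Section VII and the monitoring plan. All of this is true and lowers the stakes. However, the pilot wording sets no threshold for when testing is permitted and no rule for 2a or 4a, and case review does not compare the arms.

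Four stronger readings go too far:

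- **That non-significance will be reported as safety.** A reader might infer this because no other criterion is offered. No sentence says it.
- **That the safety tests are superiority tests that cannot flag harm.** The direction is unstated, the Pearson test is not directional in itself, and for 2a and 4a a tail toward harm would be just as natural. The blind spot exists only if the tail follows the primary outcome.
- **That adoption elsewhere hangs on these tests.** In Section VIII only the larger multi-center trial is conditional on the pilot's result. Publication and uptake by other hospitals is a separate stated intention.
- **That the one-tailed rule must go for every secondary hypothesis.** Nothing here examines labor duration, breastfeeding, satisfaction or mode of delivery.

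**Conclusion.** The plan is wrong as written for Hypotheses 2a and 4a. The method it specifies cannot support either claim, and it states no alternative. That follows from the text alone and needs no assumed rate.

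The size of the problem does rest on assumption. For land rates of 2% to 10% and a true doubling, the chance of detection toward harm runs from 0.5% to 36% at 74/37 and from 4% to 54% at 124/62, depending on the rate and on Pearson or Fisher. Only the most favorable combination, a 10% rate with every randomized woman contributing data, passes one in two.

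This should be corrected, but it ranks below a defect in the primary analysis. These are additional aims of a pilot, and the primary outcome is unaffected.

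**What to change.** In Section VII (Statistical Plan):

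1. Exempt Hypotheses 2a and 4a from the one-tailed rule. Leave the rule for the other hypotheses to be considered on its own merits.
2. For each adverse event, report counts and denominators by arm and the risk difference (waterbirth minus land) with a two-sided 95% confidence interval by Miettinen-Nurminen or Newcombe. State the upper limit as the largest excess not excluded.
3. State that p ≥ 0.05 will not be interpreted as absence of excess harm.

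In Section II, reword 2a and 4a as aims to estimate the difference in adverse outcomes between the groups.

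Estimation suits this size better than a non-inferiority test. With an assumed 5% rate in both arms, a 5-point margin, 80% power and one-sided 0.05, land n = (1.645 + 0.842)² × 0.05 × 0.95 × 1.5/0.05² ≈ 176.3, so 177 land and 354 waterbirth, 531 in all against the planned 186.

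The change costs only wording: no added participants, data or visits. The downside is a more cautious safety conclusion.
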